3.0 Background*

Music therapy has been successfully prescribed for various diseases such as anxiety, depression, neurological diseases such as epilepsy, Parkinson's disease, and multiple sclerosis.^{1,2} Music therapy and psycho-music therapy has also been beneficial in chronic lung disease such as chronic obstructive lung disease and has shown to improve symptoms of dyspnea and depression.³ Singing is based on respiratory physiology, it consists of four stages of breathing inhalation, suspension, controlled exhalation, and

recovery.⁴ The production of voice and phonation is a complex process and involves producing sound as air from the lower respiratory tract passes through the vocal cord this generates a functional connection between the lower respiratory tract and larynx ⁵. Singing is distinct from tidal breath, singing generates large lung volumes and therefore requires active exhalation compared to tidal breathing. ^{6,7} The diaphragm functions differently while singing compared to normal phonation and tidal breathing. During tidal breathing and phonation, the diaphragm is passive, whereas it is continuously contracting during singing. ^{7,8,9,10}

In the current literature benefit of music therapy in the treatment of chronic lung disease is unclear. A recent metanalysis conducted by Huang et al. showed an improvement in dyspnea and anxiety with the use of passive music(listening) along with mixed music (listening and singing) in COPD patients, The results were statistically significant although the study had a few limitations - methodology of study selection was not clearly defined; the music was selected by the subjects; and the duration of follow up was short. ¹¹ In another study conducted in Poland in 2017 by Sliwka et al. evaluated the efficacy of pulmonary rehabilitation with music therapy in patient with mild asthma. A greater increase in mean FEV1/FVC, FEF(50), and FEF(75) was observed in music therapy group with pulmonary rehabilitation compared to pulmonary rehabilitation alone, although there was an overall increase in FEV1, FEV1/FVC, (FEF(25), FEF(50), and FEF(75) in both groups.¹² Another large study conducted by Morrison et al. in 2013 followed patients for a 10-month period, 106 subjects with COPD were enrolled into a weekly community singing along with breathing exercises. After 10 months the study showed significant improvement in FEV1% and FVC% along with subject reported improvement quality of life, there was no significant improvement in dyspnea. Despite a longer period of follow up, the authors reported limitation due to no control group.¹³ Music therapy for respiratory health remains encouraging but music therapy is not routinely incorporated into pulmonary rehabilitation courses and the type of music therapy that is most effective remains indeterminate.

The objectives of our study are to a) determine whether breathing and phonation exercises improve symptoms and lung function in patient with chronic lung disease referred to pulmonary rehabilitation and b) compare two approaches to music therapy (Tonation Breathing Technique (TBT) and Music Driven Vocal Exercises (MDVE)) for feasibility and efficacy in incorporating into pulmonary rehabilitation.

We propose a pilot study to obtain preliminary data and assess feasibility of instituting music therapy into pulmonary rehabilitation. Once we establish feasibility, we will propose a larger study to compare the two approaches to music therapy as well determine the long-term effects of music therapy added to pulmonary rehabilitation.

.

References

4.0 Study Endpoints*

- 1) Specific outcomes include: subjective: Borg dyspnea score
- 2) Specific outcomes include: objective: FEV1, FVC, NIF, peak flows (all obtained from spirometry)

No specific safety outcomes are proposed, as no significant risks are associated with the proposed intervention.

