2.0 Objectives*

The objective of this study is to determine whether breathing and vocalization exercises improve dyspnea in patients who are referred for pulmonary rehabilitation (PR).

The specific aims are to determine the following:

- 1) Do breathing and vocalization exercises improve subjective pulmonary symptoms and objective pulmonary function in patients referred for PR, compared to no intervention?
 - a. Specific outcomes include: subjective: Borg dyspnea score
 - b. Specific outcomes include: objective: Forced expiratory volume in 1 second (FEV1), forced vital capacity (FVC), Peak Flow, Negative Inspiratory Force (NIF), peak flow
- 2) Do breathing and vocalization exercises improve subjective pulmonary symptoms and objective pulmonary function, compared to calm normal breathing?
 - a. Specific outcomes include: subjective: Borg dyspnea score
 - b. Specific outcomes include: objective: FEV1, FVC, NIF, peak flow
- 3) Is there a difference between two different proposed techniques of breathing and vocalization exercise techniques to improve subjective pulmonary symptoms and objective pulmonary function?
 - a. Specific outcomes include: subjective: Borg dyspnea score
 - b. Specific outcomes include: objective: FEV1, FVC, NIF, peak flow

Our hypotheses are that breathing and vocalization techniques are a) feasible; b) can improve subjective and objective pulmonary outcomes; c) there is no significant difference between the two proposed techniques of breathing and vocalization techniques.

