25.0 Resources Available

Patients are enrolled in pulmonary rehabilitation each week – approximately 16 new patients per month. They are enrolled for an 8-week period. Based on prior research studies on the same patient population, we anticipate about 50% enrollment. This is a pilot project proposal, so we propose to recruit 10 subjects initially.

PI proposed about 2.5% of FTE to the research study. Fellows will have dedicated research time to enroll subjects and collect data. Music therapy consultants will spend about 30 min/patient session (2 sessions per week x 8 weeks x 16 participants = 128 hours) on the study. They have graciously offered to provide the music therapy intervention pro bono for this pilot study. Baseline and post-rehab PFT's are clinically routine. The research spirometry proposed at 4 weeks requires funding. Investigators have been awarded a DOM Faculty Development Grant to support this expense (\$150 per spirometry x 16 participants = \$2400). Additional funding is also provided by Arts in Health operating budget. Patient incentive MetroHealth gift cards will be funded by the MH Pulmonary/Critical Care Fellows Fund through the MH Foundation.

The study will be conducted in the Pulmonary Rehabilitation center, in Hamann 3rd floor in the H&V clinic. There are dedicated rooms for education that will be used for the intervention sessions. No additional equipment will be needed.

No medical or psychological support is anticipated as needed during these sessions. There is always a physician-on-call for pulmonary rehabilitation while patients are present. If the physician-on-call is notified about a patient who is enrolled in the current study and develops any complications during the intervention, the physician-on-call will notify the PI.

All study investigators and persons assisting with the research will be given the full study protocol. We will have regular meetings to determine study progress, review study procedures, and address any issues related to the proposed study.

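### Feasibility is a stated hypothesis and the condition for the larger study, but no feasibility outcome is named and participants who miss 4 sessions are left out of analysis and count

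*Protocol*

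**What the plan says.** Feasibility appears three times as a purpose of the trial.

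- Protocol 2.0 (Objectives): "Our hypotheses are that breathing and vocalization techniques are a) feasible".
- Protocol 3.0 (Background): the two techniques are to be compared "for feasibility and efficacy in incorporating into pulmonary rehabilitation".
- Protocol 3.0 again, on what follows: "Once we establish feasibility, we will propose a larger study to compare the two approaches to music therapy".

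Section 6.0 also gives feasibility, with preliminary data, as the reason for a pilot of 16.

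The endpoints in 4.0 are of another kind. The first is "Specific outcomes include: subjective: Borg dyspnea score" and the second is "Specific outcomes include: objective: FEV1, FVC, NIF, peak flows (all obtained from spirometry". The data lists in 6.0 and 7.0 cover demographics, pulmonary history, lung function and the Borg score. The analysis paragraph in 17.0 names descriptive analyses, chi-squared tests and ANOVA, and no feasibility measure.

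Section 14.0 warns participants at 3 missed study sessions in the first 4 weeks and withdraws them at 4. Withdrawn participants are neither analysed nor counted towards the target of 16.

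**The concern.** A feasibility pilot should show whether patients can be enrolled, whether they attend, and whether they get through the sessions. Here none of these is an outcome, and the withdrawal rule removes from the counted set the participants who carry most of the information against feasibility.

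The decision to propose a larger study would then rest on whatever is assembled afterwards, from a set selected for good attendance. The comparison of TBT with MDVE on feasibility, which 3.0 promises, would have no agreed measure. Details of session completion and reasons for absence cannot be recovered reliably once the sessions are over.

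**Working it through.** **Step 1. Purpose against measurement.**

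| Place in the protocol | Feasibility content |
|---|---|
| 2.0 hypotheses | Hypothesis (a) |
| 3.0 Background | Part of the TBT and MDVE comparison; condition for the larger study |
| 6.0 Procedures | Reason for the pilot and its size |
| 1.0 objectives, 2.0 specific aims | No measure |
| 4.0 Study Endpoints | No measure: Borg, FEV1, FVC, NIF, peak flow |
| 6.0 and 7.0 data items | No session completion, no reason for a miss |
| 17.0 analysis | No measure |
| 12.0 and 25.0 | Planning figures for screening and enrolment, not criteria |
| 14.0 Withdrawal | Misses must be tracked, but those who reach the limit are excluded |

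**Step 2. The plan's own size.** 4 arms x 4 participants = 16, which reproduces the stated total. Two arms use each technique, so 2 x 4 = 8 participants per technique. No power calculation is given, by design.

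**Step 3. What 14.0 does to attendance in the counted set.** Section 6.0 gives 2 study sessions a week for 8 weeks: 2 x 8 = 16 per participant. If the limit runs over all 8 weeks, a counted participant has missed at most 3, so attendance is at least (16 - 3)/16 = 13/16 = 81%. Section 14.0 does not say clearly whether the limit of 4 covers all 8 weeks or only the first 4. If only the first 4, there are 2 x 4 = 8 sessions and the floor for that half is (8 - 3)/8 = 5/8 = 62.5%. In both cases the rule sets the floor, not the techniques.

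**Step 4. What it does to retention.** Assume that enrolment continues until 16 participants count. The number randomised is about 16 / (share not withdrawn for missed sessions). The shares below are assumed, because the protocol gives none.

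| Assumed share not withdrawn | Randomised to reach 16 counted | Withdrawals visible in the counted set |
|---|---|---|
| 90% | 16/0.9 = 17.8, about 18 | 0 |
| 80% | 16/0.8 = 20 | 0 |
| 70% | 16/0.7 = 22.9, about 23 | 0 |
| 60% | 16/0.6 = 26.7, about 27 | 0 |

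The counted set looks the same in all four rows. Only a denominator of all randomised participants tells them apart.

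**Step 5. What a feasibility proportion can deliver at this size.** Exact (Clopper-Pearson) 95% limits for x of n are the 2.5% quantile of Beta(x, n - x + 1) and the 97.5% quantile of Beta(x + 1, n - x).

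- 6 of 8: 34.9% to 96.8%.
- 7 of 8: 47.3% to 99.7%.
- 8 of 8: 63.1% to 100%.
- Both techniques pooled, 14 of 16: 61.7% to 98.4%.

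These intervals are wide, so any threshold per technique can guide a decision but cannot test one.

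**The case against.** The strongest reply is that the information will largely exist. Section 14.0 cannot operate without a count of missed sessions for each participant. Screening and consent leave records, the payments in 13.0 mark completion, and measurements fall due at weeks 4 and 8. Section 4.0 says that outcomes include those listed, and 1.0 names breath hold and quality of life, which 4.0 omits, so 4.0 may not be exhaustive. Definitions and cut-offs could also sit in an analysis plan that is not shown.

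Much of this stands. A reader might infer that neither technique can be judged feasible or infeasible at all. The documents do not support that, because a partial description from by-product counts is possible.

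Two things survive the reply. First, an analysis plan cannot analyse what is not collected, and completion within a session and reasons for absence are in none of the data lists. Second, 14.0 is a protocol rule that itself settles who is analysed and counted. An analysis plan that restored those participants would contradict it.

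It is also fair to say that Borg is the primary objective in 1.0 and that all three specific aims in 2.0 concern symptoms and lung function. Nothing here requires feasibility to displace it.

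**Conclusion.** The point holds in a limited form. Feasibility is a hypothesis, part of an objective and the condition for the next study, yet it has no named outcome. The exclusion in 14.0 makes the counted set look more adherent than the randomised one: attendance of at least 81% and no withdrawals for missed sessions, by construction. The 81% assumes 2 sessions a week and a limit applied over 8 weeks. The retention table assumes that uncounted participants are replaced.

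Some stronger readings are tempting but do not follow.

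- *Conflicting enrolment rates.* The 16 of 40 in 12.0 (40%) and the 50% in 25.0 need not disagree. The first is a share of those screened, and the second is stated without a denominator. Since 16 of 40 is a planning figure, an interval around it would show nothing.
- *A contradiction on safety.* Section 4.0 says "No specific safety outcomes are proposed, as no significant risks are associated with the proposed intervention", and 25.0 covers the case in which a participant "develops any complications during the intervention, the physician-on-call will notify the PI". The latter is conditional and follows a statement that no support is expected to be needed, so the two are compatible.
- *Efficacy results cannot inform feasibility because significance is not expected.* The reason is simpler: they measure something else.

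The change should be made before the first participant. It concerns the pilot's main deliverable, not patient safety.

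**What to change.** Add feasibility to 4.0 as a named endpoint alongside Borg, with three measures:

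1. Participants enrolled divided by eligible patients approached, overall.
2. Sessions attended and sessions completed in full, tabulated separately for the TBT, MDVE and normal-breathing periods. The separation matters because each participant spends 4 of the 8 weeks on normal breathing.
3. The share of all randomised participants who complete 8 weeks without reaching the existing limit of 4 missed sessions, by assigned technique.

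Amend 14.0 so that withdrawn participants are kept and counted in these feasibility analyses. The withdrawal rule itself need not change, but the period over which the 4 misses are counted should be made explicit.

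Add one REDCap line per session: attended, completed, reason if not. For 16 participants this is 16 x 16 = 256 short entries. Section 25.0 already budgets a consultant for 2 sessions a week over all 8 weeks, so someone is present to make them.

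State before the first participant the values at which the sponsor would proceed. Present them as descriptive, with exact intervals, given about 8 participants per technique.

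The cost is protocol wording, a few minutes of entry per session, and the possibility that a technique looks less feasible than it would have in the counted set.

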Pulmonary function testing is standard for all patients who receive PR – testing before and after PR is routine clinical course. We propose an additional PFT study at 4 weeks, as part of the research protocol (covered by the Department of Medicine funding)

In summary, the interventions for research purposes will include:

- 1) 20-minute sessions after PR for intervention (TBT or MDVE) or normal breathing for twice a week for the 8 weeks they are participating in PR.
- 2) PFT at end of week 4

Proposed subjective outcomes are routinely asked of PR patients, but will be collected at baseline, at 4 weeks (mid-way), and at 8 weeks (end) of PR.

Proposed objective outcomes:

- 1) For FEV1, FVC – these are routinely collected at baseline and at end of PR. We propose an additional PFT study at 4 weeks, covered by the DOM Faculty Development Fund.
- 2) For peak flow and NIF – these are procedures that ask for patient to breathe maximally for inspiration and expiration. They are not routine measures collected but are routine bedside measurements for pulmonary patients that can be collected for any person without any additional risk or cost.

Data will be obtained as following:

- 1) Routinely obtained information will be collected from EPIC into a REDCap database. This includes:
 - a. Patient demographics – name, MRN, DOB, sex, gender, race, ethnicity, height, weight, BMI,
 - b. Pulmonary history: reason for PR referral (routine collection); date of symptom onset; date of diagnosis of lung pathology; prior PFT findings – FEV1, FVC, peak flow, NIF.
 - c. PR questionnaire info: Borg dyspnea score at baseline and each visit (routine collection)

There are no plans for long-term follow-up.

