9.0 Study Timelines*

An individual participants time in the study will be approximately 8 weeks.

Time 0 – Informed Consent signed.

Weeks 1-8 – normal Pulmonary Rehabilitation 3 times a week, with phonation intervention (TBT or MDVE) or silent breathing time.

On last session of week 4 and week 8: PFT's, NIF, VC, peak flows will be measured. Borg dyspnea scale will be collected.

We hope to collect 16 participants for this study by November 2022, and have primary analysis completed by December 2022 for submission to American Thoracic Society 2023 presentation.

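### NIF and peak flow come from spirometry in section 4.0 but from the bedside in section 6.0, so a baseline taken from the record may not match the follow-up method

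*Protocol*

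**What the plan says.** The protocol describes the source of these two outcomes in four places.

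- **Section 4.0 (Study Endpoints)** gives one source for all four objective outcomes: "FEV1, FVC, NIF, peak flows (all obtained from spirometry".
- **Section 6.0 (Procedures Involved), objective outcomes**, separates them. FEV1 and FVC belong to the lung function test: "For FEV1, FVC – these are routinely collected at baseline and at end of PR", with a research test added at week 4. The other two are described differently: "For peak flow and NIF – these are procedures that ask for patient to breathe maximally for inspiration and expiration", and "They are not routine measures collected but are routine bedside measurements for pulmonary patients".
- **Section 6.0, data to be obtained**, then puts both under information routinely drawn from the electronic record: "prior PFT findings – FEV1, FVC, peak flow, NIF". Section 7.0, item 7.2, repeats this.
- **Section 9.0 (Study Timelines)** has for the start only "Time 0 – Informed Consent signed". The measurements come later: "On last session of week 4 and week 8: PFT's, NIF, VC, peak flows will be measured".

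Section 10.0 requires a baseline lung function test to be on file. It does not say that the test must include NIF or peak flow. No section requires one device or method across time points.

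**The concern.** The endpoint section and the procedures section name different sources for the same two outcomes, and for NIF the endpoint section cannot be followed. NIF is negative inspiratory force, a pressure. Spirometry measures volume and flow. Peak flow can be read from a spirometer or from a bedside meter, so its definition depends on which section staff follow.

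This matters because of where a baseline value would come from. The only source the protocol names before week 4 is the record, as part of an earlier lung function test. The values at weeks 4 and 8 are described as bedside measurements. A change from baseline could then contain a difference between methods as well as any change in the patient. NIF is a named secondary objective in section 1.0, and both measures are outcomes under all three aims in section 2.0. The pilot is meant to supply preliminary data for a larger study, so a method shift in these change scores could be carried into its planning.

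**Working it through.** The protocol states no figure on this point, so there is none to reproduce. The check sets the texts side by side and then follows an offset through the analyses.

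**Source at each time point, as written**

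- Baseline: earlier lung function results in the record (sections 6.0, 7.0 and 10.0). Section 9.0 names nothing but consent at time 0.
- Week 4: bedside (section 6.0) or spirometry (section 4.0).
- Week 8: the same list of measurements as at week 4 (section 9.0).

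The text therefore allows a laboratory baseline with bedside follow-up. It gives no reason to expect a change of method between weeks 4 and 8.

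**Inputs**

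- D: a constant difference, bedside minus laboratory. This is an assumption; the documents give no size, so results are in units of D.
- 16 participants, 4 in each of 4 arms (section 6.0). Two arms start with a technique and two with normal breathing, so the plan has 4 + 4 = 8 in each order.

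**Effect of D for a participant with a laboratory baseline and bedside follow-up**

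- Week 4 minus baseline: error D.
- Week 8 minus baseline: error D.
- Week 8 minus week 4: D − D = 0.

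**Comparison between arms over the same interval**

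Each arm's mean change carries the same D, so the difference carries D − D = 0. This holds on average under randomisation, when a mismatched baseline is equally likely in every arm.

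**Pooled within-patient contrast** (change in the technique period minus change in the normal-breathing period)

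- Technique first: D − 0 = +D.
- Normal breathing first: 0 − D = −D.
- Mean error: D × (n1 − n2)/(n1 + n2), where n1 is the number with technique first and n2 the number with normal breathing first, among participants who have such a baseline.

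If all 16 have one, the size of the error is:

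- 8:8 gives D × 0/16 = 0
- 7:9 gives D × 2/16 = 0.125D
- 6:10 gives D × 4/16 = 0.25D
- 4:12 gives D × 8/16 = 0.5D

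**How likely is imbalance?**

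Section 6.0 plans 4 per arm but describes only a random number generator giving 1 to 4. If that means unrestricted allocation (an assumption), the order is a fair coin for each participant:

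- P(8:8) = C(16,8)/2^16 = 12,870/65,536 = 19.6%
- P(6:10 or worse) = 2 × 14,893/65,536 = 45.4%

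If the 4 per arm is enforced, the order is 8:8 and the error in this contrast is zero, provided that recorded baselines are equally common in both orders.

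**The case against.** The strongest reply is that this is loose wording with little effect on the trial's comparisons. Much of that stands.

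- The aims in section 2.0 are comparative. A common offset cancels on average between arms over the same interval, and cancels in the pooled within-patient contrast at the planned allocation.
- Section 6.0 names no device. It does not say that bedside peak flow is taken on an instrument other than the spirometer, so a mismatch is possible rather than stated.
- The primary outcome is the Borg score. Section 1.0 does not list peak flow among the secondary objectives, and section 17.0 expects no significant results from a sample this small.

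A reader might also draw three stronger conclusions, which the documents do not support:

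- **That weeks 4 and 8 use different instruments.** Section 9.0 sets the same list for both visits, and nothing suggests that the method changes between them.
- **That every participant's change is wrong by D.** Section 6.0 says these measures are not routinely collected, so some participants may have no recorded value. They have a missing baseline, not a mismatched one.
- **That NIF will not be obtained because section 4.0 assigns it to spirometry.** Section 6.0 describes a maximal-effort procedure and section 9.0 schedules NIF at weeks 4 and 8. Section 4.0 is wrong for NIF, but the measurement is planned.

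What remains is that sections 4.0 and 6.0 cannot both be right, and that no section fixes one method from baseline to week 8.

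**Conclusion.** The contradiction is real and its consequence is limited; severity is minor. Section 4.0 gives a source for NIF that cannot produce it, and a source for peak flow that section 6.0 does not share. As written, a baseline value, where one exists, can come from an earlier laboratory test and the follow-up values from the bedside.

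For those participants an offset D enters the change from baseline in full. It enters a pooled within-patient contrast only in proportion to the imbalance between orders: zero at 8:8 and 0.25D at 6:10. It does not affect the difference between weeks 4 and 8, comparisons between arms over the same interval (on average), or the Borg score.

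This rests on D being constant and on baselines being taken from the record. The documents give no size for D, so the error cannot be put in L/min or in pressure units.

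**What to change.** Reconcile sections 4.0, 6.0, 7.0 (item 7.2) and 9.0:

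- Take NIF out of the statement in section 4.0 that all objective outcomes come from spirometry.
- Define peak flow by one method at baseline, week 4 and week 8. The simplest choice is the spirometry already planned at each of these points. A baseline test already on file may have used a different spirometer, so this aligns the method but does not guarantee the same device. A bedside peak flow at all three points would also be consistent.
- Measure NIF by one bedside pressure method at all three points, and add it to section 9.0 at the first rehabilitation visit.
- If a baseline NIF is not added, restrict the NIF analysis to comparisons of the week 4 and week 8 values.
- Ask the sponsor to confirm what VC means in section 9.0, since the other sections use FVC.

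The cost is wording plus one short extra NIF measurement per participant, which section 6.0 says adds neither risk nor cost. Peak flow from spirometry needs no new test.
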